The safety analysis population will be the Safety population in each cohort consisting of all patients who received at least one dose of study medication.

Determination of Sample Size

The purpose of this Phase II study is estimation and hypothesis generation regarding the effect of cobimetinib plus atezolizumab on CNS metastases from BRAF^{V600} wild-type melanoma and the effect of cobimetinib plus atezolizumab and vemurafenib on CNS metastases from BRAF^{V600} mutation-positive melanoma. The 15 patients enrolled into the BRAF^{V600} wild-type cohort at the time of recruitment stop will be analysed descriptively only. There are no reference data available on the use of these combination therapies in these patient populations.

There is no formal statistical hypothesis in this study. The originally planned total sample size of approximately 60 patients per cohort was based on an estimated study drop-out rate of 15%, the primary endpoint and 95% confidence intervals (CIs) for each treatment regimen. No power calculation has been performed.

In a Dear Investigator Letter dated 9 July 2019, the Sponsor communicated the decision to discontinue enrollment in the BRAF^{V600} wild-type cohort (Cohort 1). As of 9 July 2019, 15 patients were enrolled in Cohort 1.

Point estimates and 95% CIs for a range of possible outcomes produced using nQuery (version 7) with 50 evaluable patients in the BRAF^{V600} mutation-positive cohort are provided below.

Intracranial Response Rate in Cohort 2	95% Confidence Interval
35%	(21.8%, 48.2%)
40%	(26.4%, 53.6%)
45%	(31.2%, 58.8%)
50%	(36.1%, 63.9%)
55%	(41.2%, 68.8%)

Interim Analyses

A safety interim analysis will be performed by the Sponsor and reviewed by the IMC after at least 10 patients in both cohorts have completed their first tumour assessment (i.e., approximately eight weeks after the start of study treatment). The analysis will be conducted by the Sponsor according to the Sponsor's standard operating procedures for safety reviews. The conduct of the IMC safety interim review will be as described in the IMC charter.

LIST OF ABBREVIATIONS AND DEFINITIONS OF TERMS

Abbreviation	Definition
ALT	alanine aminotransferase
ALP	alkaline phosphatase
aPTT	activated partial thromboplastin time
AST	aspartate transaminase (aspartate aminotransferase)
AUC	under the concentration-time curve
BID	twice daily
BRAF ^{V600}	V600 codon of the BRAF oncogene
CHMP	Committee for Medicinal Products Human Use
CI	confidence interval
CR	complete response
CrCl	creatinine clearance
CRO	contract research organization
CRS	cytokine-release syndrome
CT	computed tomography
CTCAE	Common Terminology Criteria for Adverse Events
CNS	central nervous system
COPD	chronic obstructive pulmonary disease
COVID-19	coronavirus disease 2019
CPK	creatine phosphokinase
CTLA-4	cytotoxic T-lymphocyte-associated antigen 4
cuSCC	cutaneous squamous cell carcinoma
DCR	disease control rate
DNA	deoxyribonucleic acid
DOR	duration of response
EC	Ethics Committee
ECG	electrocardiogram
eCRF	electronic Case Report Form
ECOG	Eastern Cooperative Oncology Group
EDC	electronic data capture
EORTC	European Organisation for Research and Treatment of Cancer
FSH	follicle-stimulating hormone
GHS	Global Health Status
HBcAb	hepatitis B core antibody
HBsAg	hepatitis B surface antigen
HBV	hepatitis B virus
HCV	hepatitis C virus

Abbreviation	Definition
HEENT	head, eyes, ears, nose, throat
HIV	human immunodeficiency virus
HLH	hemophagocytic lymphohistiocytosis
HRQoL	health-related quality of life
ICH	International Council for Harmonisation
IFN- α	interferon- α
IL-2	interleukin-2
IMC	Internal Monitoring Committee
IMP	investigational medicinal product
INR	international normalised ratio
iRANO	immunotherapy Response Assessment for Neuro-Oncology
IRB	Institutional Review Board
IRC	Independent Review Committee
IRR	infusion-related reaction
IV	intravenous(ly)
LPI	last patient in
LVEF	left ventricular ejection fraction
MAPK	RAS/RAF/MEK/ERK mitogen-activated protein kinase (cascade)
MAS	macrophage activation syndrome
MRI	magnetic resonance imaging
NCCN	National Comprehensive Cancer Network
NCI	National Cancer Institute
NGS	next-generation sequencing
NSAID	non-steroidal anti-inflammatory drug
NSCLC	non-small cell lung cancer
OCT	optical coherence tomography
ORR	objective response rate
OS	overall survival
PD-1	programmed death 1
PD-L1	programmed death ligand 1
PET	positron emission tomography
PFS	progression-free survival
PO	orally
PR	partial response
PRO	patient-reported outcome
QD	once-daily (or once a day)
Q2W	every two weeks
Q3W	every three weeks

Abbreviation	Definition
QLQ-C30	Quality-of-Life Questionnaire Core 30
QLQ-BN20	Quality-of-Life Questionnaire brain cancer module
QTcF	QTc interval corrected using Fridericia's method
RBR	Research Biosample Repository
RECIST	Response Evaluation Criteria in Solid Tumors
RVO	retinal vein occlusion
SAE	serious adverse event
SARS-CoV-2	severe acute respiratory syndrome coronavirus 2
SC	Steering Committee
SCC	squamous cell carcinoma
SD	stable disease
SITC	Society for Immunotherapy of Cancer
SmPC	Summary of Product Characteristics
SRT	stereotactic radiotherapy
ULN	upper limit of normal
WBRT	whole brain radiation
WES	whole exome sequencing
WGS	whole genome sequencing

1. **BACKGROUND**

1.1 **BACKGROUND ON MELANOMA AND MELANOMA WITH CENTRAL NERVOUS SYSTEM METASTASES**

In 2012, the worldwide incidence of cutaneous melanoma is estimated to have been more than 232 000 cases with approximately 55 500 associated deaths. The highest per capita incidence and mortality rates were observed in Australia/New Zealand (14 738 cases, 2019 deaths), Europe (100 442 cases, 22 211 deaths) and North America (74 515 cases, 11 343 deaths) ([Ferlay et al. 2013](#)). The number of melanoma cases worldwide is increasing with some countries reporting at least doubling of melanoma incidence over the last two decades particularly within fair-skinned populations ([Australian Institute of Health and Welfare 2016](#), [Centers for Disease Control and Prevention 2015](#), [World Health Organization 2018](#)).

Cutaneous melanoma arises from melanocyte cells of skin. If recognized early, primary lesions can be excised without significant sequelae. Once metastatic however, the disease is characterized by mortality and morbidity. Until recently, treatment options for metastatic melanoma were limited. Dacarbazine was considered to be the standard first-line treatment; however, outcomes were poor, with response rates of 5–12%, median progression-free survival (PFS) of less than two months, and median overall survival (OS) of 6.4 to 9.1 months ([Middleton et al. 2000](#); [Bedikian et al. 2006](#); [Chapman et al. 2011](#); [Robert et al. 2011](#)). Combination chemotherapy and chemotherapy combined with interferon- α (IFN- α) or interleukin-2 (IL-2), although showing improved response rates, did not result in improved OS ([Chapman et al. 1999](#); [Ives et al. 2007](#)).

Unfortunately, brain metastases are common in melanoma. Central nervous system (CNS) disease detected due to symptoms or surveillance imaging occurs in approximately 37–44% of metastatic patients and autopsy studies show brain metastases in 75% of fatal melanoma cases ([Sloan et al. 2009](#), [Goyal et al. 2015](#)). Brain metastases represent a unique therapeutic challenge due to limitations in drug delivery across the blood-brain barrier ([Agarwala et al. 2000](#)). Surgery, whole brain radiation (WBRT) and stereotactic radiotherapy (SRT) have been mainstays of melanoma brain metastases treatment, but these approaches do not dramatically ameliorate outcomes as shown by a median OS of 6.7 months determined in a retrospective analysis of this patient population ([Sperduto et al. 2012](#)). Difficulties in treating melanoma brain metastases patients are exacerbated by their exclusion from large clinical trials ([Larkin et al. 2015](#), [Long et al. 2015](#), [Robert et al. 2015a](#), [Robert et al. 2015b](#), [Ascierto et al. 2016](#)).

The RAS/RAF/MEK/ERK mitogen-activated protein kinase (MAPK) cascade is a key intracellular signalling network that transduces multiple proliferative and differentiating signals from the extracellular environment to cell nuclei to activate cellular growth and differentiation ([Johnson and Lapadat 2002](#), [Roberts and Der 2007](#)). Mutations in the V600 codon of the BRAF oncogene (BRAF^{V600}) occur in approximately 50% of all

cutaneous melanomas and, though mostly mutually exclusive to these BRAF mutations, NRAS is mutated in 15–25% of melanomas (Davies et al. 2002, Lee et al. 2011, Goel et al. 2006). These BRAF and NRAS mutations trigger constitutive activation of the MAPK pathway resulting in growth factor-independent cellular proliferation and survival characteristic of oncogenesis. Notably, the presence of BRAF mutations has been associated with an increased risk of CNS metastases in patients with advanced melanoma as indicated by a 24% rate of CNS metastases in BRAF mutation-positive melanoma versus a 12% rate in patients with BRAF wild-type disease (Jakob et al. 2012).

In the last decade, immunotherapies disrupting cytotoxic T-lymphocyte–associated antigen 4 (CTLA-4) and programmed death 1 (PD-1) pathways as well as agents targeting the MAPK pathway have been introduced into the treatment of advanced melanoma leading to improved outcomes. In one large randomized study comparing PD-1 pathway blockade with pembrolizumab to CTLA-4 blockade with ipilimumab, 24-month survival rates of 55% were observed (Schachter et al. 2017). In studies of BRAF inhibitors alone or combined with MEK inhibitors in patients with BRAF^{V600} mutations, OS of 22.3 to 25.1 months were observed (McArthur et al. 2014, Long et al. 2015).

The activity of these agents in melanoma brain metastases has been shown in clinical trials limited to patients with CNS disease. In a study of PD-1 pathway blockade with pembrolizumab, intracranial responses were observed in 4/18 (22%) of melanoma patients enrolled. A tolerable safety profile was observed (Goldberg et al. 2016). In an open-label trial comparing nivolumab (an anti-PD-1 monoclonal antibody) with or without ipilimumab in patients unselected for BRAF mutation, at a median follow-up of 16.4 months, complete or partial intracranial responses were observed in 11/26 (42%) patients receiving both agents and 5/25 (20%) patients receiving nivolumab alone. PFS at six months was 46% and 29% respectively (Long et al. 2017). Combined nivolumab/ipilimumab showed similar activity in another single arm trial with an intracranial objective response rate (ORR) of 55% and 6-month PFS greater than 60% at 9 months median follow-up in 75 patients (Tawbi et al. 2017). No new or unexpected adverse events were observed in these studies.

In a clinical trial of 146 patients with BRAF^{V600} mutation-positive disease (n=90 with no prior treatment for brain metastases, n=56 with prior treatment for brain metastases), MAPK pathway disruption via BRAF inhibition with vemurafenib (Zelboraf®) produced an intracranial ORR of 18% in both prior treated and untreated patient cohorts. Median OS was 9.6 months (range 0.6–34.5) in the prior treatment cohort and 8.9 months (range 0.7–34.3) in the cohort of patients who had not received prior treatment for brain metastases. Study treatment was reported as well tolerated (McArthur et al. 2017). In a study of dual MAPK pathway blockade with combined BRAF and MEK inhibition with dabrafenib (a BRAF inhibitor) and trametinib (a MEK inhibitor) in patients with BRAF^{V600} mutation-positive disease, intracranial responses were observed in 58% of the patients

Cobimetinib, atezolizumab, vemurafenib — F. Hoffmann-La Roche Ltd

32 / Protocol MO39136, Version 5.0

with asymptomatic disease and no prior treatment. Preliminary OS analyses in this patient subset found median survival ranging from approximately 10 to 24 months. No unexpected safety issues were observed ([Davies et al. 2017](#)).

These results suggest that immunotherapy and BRAF-MEK targeted approaches may provide systemic alternatives to established, but arguably inadequate, local methods for treating melanoma patients with intracranial disease.

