- Able to comply with the study protocol, in the investigator's judgment
- ECOG Performance Status \leq 2
- Life expectancy of > 3 months
- Willing and able to complete health and quality of life questionnaires required by the protocol
- Adequate hematologic and end-organ function, defined using the following laboratory results obtained within 14 days prior to first dose of study treatment with the exception of amylase and lipase which may be obtained within 28 days prior to study treatment initiation:
 - Absolute neutrophil count $\geq 1.5 \times 10^9/L$ without granulocyte colony-stimulating factor support
 - White blood cell count $\geq 2.5 \times 10^9/L$
 - Lymphocyte count $\geq 0.5 \times 10^9/L$
 - Platelet count $\geq 100 \times 10^9/L$ without transfusion
 - Haemoglobin $\geq 90 \text{ g/L}$ without transfusion
 - Serum albumin $\geq 25 \text{ g/L}$
 - Total bilirubin $\leq 1.5 \times$ upper limit of normal (ULN)
 - Aspartate transaminase and alanine aminotransferase $\leq 2.0 \times$ ULN, or for patients with documented liver metastases, ≤ 5.0 ULN
 - *For patients assigned to Cohort 2 only:* Amylase and lipase $\leq 1.5 \times$ ULN
 - Alkaline phosphatase (ALP) $\leq 2.5 \times$ ULN or, for patients with documented liver or bone metastases ALP $\leq 5 \times$ ULN
 - Serum creatinine $\leq 1.5 \times$ ULN or creatinine clearance (CrCl) $\geq 40 \text{ mL/min}$ on the basis of measured CrCl from a 24-hour urine collection or Cockcroft-Gault glomerular filtration rate estimation as follows:

$$\text{CrCl} = \frac{(140 - \text{age}) \times (\text{weight in kg}) (\times 0.85 \text{ if female})}{72 \times (\text{serum creatinine in mg/dL})}$$

- For patients not receiving therapeutic anticoagulation: international normalised ratio (INR) or activated partial thromboplastin time (aPTT) $\leq 1.5 \times$ ULN within 28 days prior to initiation of study treatment
For patients receiving therapeutic anticoagulation: stable anticoagulant regimen that does not include coumarin anticoagulants, stable INR, and stable aPTT during the 28 days immediately preceding initiation of study treatment
- Female patients of childbearing potential and male patients with partners of childbearing potential must agree to always use two effective forms of contraception including at least one method with a failure rate of $< 1\%$ per year during the course of this study and for at least six months after completion of study therapy.

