 - Females of childbearing potential are defined as sexually mature women without prior oophorectomy or hysterectomy who have had menses within the last 12 months.
 - Females are not considered to be of childbearing potential if amenorrhoeic for > 12 months and follicle-stimulating hormone (FSH) level $\geq 40 \text{ IU/L}$. For females who have been amenorrhoeic for ≥ 2 years, the requirement for FSH measurement at screening will be waived.

- Examples of effective contraception methods with a failure rate of < 1% per year include bilateral tubal ligation and male surgical sterilization; hormonal contraceptives that inhibit ovulation, hormone-releasing intrauterine devices; and copper intrauterine devices. A reliable barrier method may be used as the second contraceptive method. Hormonal contraceptive methods must be supplemented by a barrier method. Please note that potential interactions between vemurafenib and hormonal contraceptives may decrease the effectiveness of hormonal contraceptives.
- Male patients who are surgically sterilized are required to use barrier methods of contraception.
- Female patients of childbearing potential must agree to refrain from donating eggs during the course of the study and for at least 5 months after their final dose of atezolizumab
- Male patients must agree to refrain from donating sperm during the course of the study and for at least six months after the last dose of cobimetinib

Exclusion Criteria

Patients who meet any of the following cancer-related or general criteria will be excluded from study entry:

Cancer-related criteria

- Ocular melanoma
- Leptomeningeal involvement
- Uncontrolled tumour-related pain

Patients requiring narcotic pain medication must be on a stable regimen at start of study treatment.

Symptomatic lesions amenable to palliative radiotherapy (e.g., bone metastases or metastases causing nerve impingement) should be treated prior to enrollment. Patients should be recovered from the effects of radiation. There is no required minimum recovery period.

Asymptomatic metastatic lesions that would likely cause functional deficits or intractable pain with further growth (e.g., epidural metastasis that is not currently associated with spinal cord compression) should be considered for loco-regional therapy, if appropriate, prior to enrollment.

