4.5.9 Laboratory, Biomarker and Other Biological Samples

Samples for the following laboratory tests will be sent to the study site's local laboratory for analysis:

- BRAF^{V600} mutation status determined in tumour tissue by a validated genetic test
- Haematology: white blood cell count, red blood cell count, haemoglobin, haematocrit, reticulocyte count, platelet count, differential count (neutrophils, eosinophils, basophils, monocytes, lymphocytes, other cells).
- Chemistry panel (serum or plasma): sodium, potassium, magnesium, chloride, bicarbonate or total carbon dioxide (bicarbonate and total carbon dioxide are not mandatory if unavailable at site), glucose (non-fasting), BUN or urea, creatinine, albumin, phosphorus, calcium, total bilirubin, ALP, ALT, AST, lactate dehydrogenase and CPK, amylase and lipase.
- Both blood glucose and lipid panel must be obtained after at least an 8-hour fast, at screening only. Lipid panel should include total cholesterol, low-density lipoprotein and triglycerides.
- Urinalysis includes dipstick (pH, specific gravity, glucose, protein, ketones, blood) and microscopic examination (sediment, RBCs, WBCs, casts, crystals, epithelial cells, bacteria).
- Coagulation: INR, aPTT
- Thyroid function testing: thyroid-stimulating hormone, free T3 (or total T3 for sites where free T3 is not performed), free thyroxine.
- HBV serology: HBsAg, hepatitis B surface antibody, total HBcAb. If a patient has a negative HBsAg test and a positive total HBcAb test at screening, an HBV DNA test should be performed at screening.
- HCV serology: HCV antibody and (if HCV antibody test is positive) HCV RNA. If a patient has a positive HCV antibody test at screening, an HCV RNA test must also be performed to determine if the patient has an active HCV infection.
- HIV serology
- Pregnancy test: All women of childbearing potential will have a negative serum pregnancy test within seven days prior to initiation of study treatment. Urine pregnancy tests (serum pregnancy test if urine test is not available) will be performed at specified subsequent visits. If a urine pregnancy test is positive, it must be confirmed by a serum pregnancy test.

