- m. Chemistry panel (serum or plasma) includes sodium, potassium, magnesium, chloride, bicarbonate or total carbon dioxide (bicarbonate and total carbon dioxide are not mandatory if unavailable at site), glucose (non-fasting), BUN or urea, creatinine, albumin, phosphorus, calcium, total bilirubin, ALP, ALT, AST, lactate dehydrogenase and CPK, amylase and lipase. If screening blood chemistry is performed within 7 days of initiation of study treatment, it does not need to be repeated for Day 1 of Cycle 1.
- n. All women of childbearing potential will have a negative serum pregnancy test within seven days prior to initiation of study treatment. Women without prior oophorectomy or hysterectomy who have been amenorrhoeic for >12 months but < 2 years must have a FSH level test to determine childbearing potential. Urine pregnancy tests will be performed on Day 1 of each treatment cycle, at the treatment discontinuation visit and at study follow up until six months post-study treatment discontinuation. If a urine pregnancy test is positive, it must be confirmed by a serum pregnancy test.
- o. Includes thyroid-stimulating hormone, free T3 (or total T3 for sites where free T3 is not performed), free thyroxine. Thyroid-function tests are to be performed at screening, on Day 1 of Cycles 1-5 and every second cycle thereafter (e.g., Day 1 of Cycles 7, 9, 11, etc.), and at the treatment discontinuation visit.
- p. Both blood glucose and lipid panel must be obtained after at least an 8-hour fast, at screening only. Lipid panel should include total cholesterol, low-density lipoprotein and triglycerides
- q. Urinalysis includes dipstick (pH, specific gravity, glucose, protein, ketones, blood) and microscopic examination (sediment, RBCs, WBCs, casts, crystals, epithelial cells, bacteria).
- r. Ophthalmologic examinations should be performed at screening; on Day 1 of Cycle 2 (\pm 1 week), Cycles 5, 8, 11, 15, 19, 23, and every six cycles thereafter (i.e., Cycles 29, 35, 41, etc.) (\pm 2 weeks for each); at the treatment discontinuation visit; and as clinically indicated (including in the event of any visual changes).

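### The childbearing-potential definition ignores why menses stopped, so a woman amenorrhoeic for two years or more on a hormonal contraceptive falls outside it with FSH waived and no pregnancy test ordered

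*Protocol*

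**What the plan says.** The definition stands in the Protocol Synopsis (Inclusion Criteria, general) and is repeated in Sections 4.1.1 and 4.5.9: "Females of childbearing potential are defined as sexually mature women without prior oophorectomy or hysterectomy who have had menses within the last 12 months". A companion rule takes a woman out of childbearing potential if she has been amenorrhoeic for more than 12 months and her FSH is at least 40 IU/L. From two years of amenorrhoea, "the requirement for FSH measurement at screening will be waived". Note n of Appendix 1 and note o of Appendix 2 match this: women amenorrhoeic for more than 12 months but less than two years "must have a FSH level test to determine childbearing potential". None of these places says what the cause of the amenorrhoea must be, and none sets an age.

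Several duties depend on the definition. For contraception, "Female patients of childbearing potential and male patients with partners of childbearing potential must agree to always use two effective forms of contraception". For testing, Section 4.5.9 says "All women of childbearing potential will have a negative serum pregnancy test within seven days prior to initiation of study treatment", and Section 4.1.2 repeats this. Notes n and o then schedule urine tests on Day 1 of each cycle, at the discontinuation visit and in follow-up to six months.

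The same inclusion criterion lists among its acceptable methods "hormonal contraceptives that inhibit ovulation, hormone-releasing intrauterine devices". It warns that "potential interactions between vemurafenib and hormonal contraceptives may decrease the effectiveness of hormonal contraceptives", and adds: "Hormonal contraceptive methods must be supplemented by a barrier method".

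**The concern.** The rule uses absence of menses as a stand-in for menopause, but it does not exclude the other obvious reason for absent menses, a contraceptive that suppresses them. The protocol accepts such contraceptives, and Section 4.4.1 tells users of oral contraceptives to carry on. A fertile woman can therefore be classed with postmenopausal women because of the contraceptive she relies on.

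She is also a woman whose method the protocol regards as less secure in Cohort 2, since it expects that vemurafenib may weaken hormonal contraception. Section 5.1.1.9 reports embryo lethality and foetal malformations with cobimetinib in rats, at systemic exposures similar to those in patients on 60 mg, and advises against use in pregnancy. At stake are prevention and early detection of foetal exposure in a small group. The estimate of intracranial response and the other analyses are not touched.

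**Working it through.** The plan gives no figure to reproduce, so the check is to apply its text to one case: intact ovaries and uterus, with amenorrhoea caused by a hormonal method.

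**Classification by time since last menses**

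| Time | Meets the definition? | FSH ordered? | Outcome |
|---|---|---|---|
| Up to 12 months | Yes | Not needed | Of childbearing potential; all duties apply |
| Over 12 months, under 2 years | No | Yes (notes n and o) | Taken out only if FSH is at least 40 IU/L |
| 2 years or more | No | No (waived) | Outside the definition, with no test that could reclassify her |

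The gap is specific to the third row. It does not depend on how the waiver is read, because without menses in the past 12 months she already fails the positive definition. The waiver removes the one check that could correct this.

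**What follows for her**

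- Serum pregnancy test (4.1.2, 4.5.9): limited to women of childbearing potential, so not ordered.
- Urine tests (note o): the sentence names no group, but the note opens with women of childbearing potential. In context, not ordered.
- Egg-donation rule (4.1.1): limited to the same group, so it does not apply.
- Consent-form instruction to tell the investigator of a pregnancy (5.4.3.1): also limited to that group, so it does not apply.
- Two methods of contraception (4.1.1): limited to that group. The barrier sentence beneath it is framed by method, so its reach to her is arguable.

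**Size.** The documents give no sex or age mix and no contraceptive use. Assumed for the approximately 60 Cohort 2 patients: 30% to 50% women, of whom 2% to 10% have been amenorrhoeic for two years or more on a hormonal method.

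- Low: 60 × 0.30 × 0.02 = 0.36 women.
- High: 60 × 0.50 × 0.10 = 3.0 women.

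For a woman treated for k cycles (k assumed to be 2, 6 or 12), tests not ordered up to and including the discontinuation visit = 1 serum + k urine on Day 1 of each cycle + 1 at discontinuation = k + 2:

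- k = 2: 4; k = 6: 8; k = 12: 14.
- Across the trial: 0.36 × 4 = 1.4 to 3.0 × 14 = 42.

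Follow-up tests are left out. Note o gives no number for them, and follow-up contacts may be by telephone.

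Time over which the two-method duty is in doubt = 28k days of treatment + 183 days (six months afterwards):

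- k = 2: 56 + 183 = 239 days.
- k = 6: 168 + 183 = 351 days.
- k = 12: 336 + 183 = 519 days.

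These figures describe missing duties and tests. They are not a risk of pregnancy.

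**The case against.** The best case for the protocol is that she is better covered than the definition alone suggests.

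- **Section 4.4.1** says patients of reproductive potential should use highly effective contraception. That term is not tied to menses, and its ordinary meaning fits her. This stands as a softening. But it is a recommendation, the term is undefined, it refers back to Section 4.1.1, and it orders no test.
- **The barrier sentence** is mandatory and speaks of methods, and by hypothesis she uses a hormonal one. A reader might infer from the definition that the second-method duty is removed outright. The text does not support that; the duty is unclear, because the sentence sits under a criterion for patients of childbearing potential. On the generous reading, testing is still missing.
- **Notes n and o** order FSH for women with no menses for over 12 months, which would be pointless if the positive definition were exhaustive. The protocol evidently means a menopause screen, and the waiver does not forbid a test. That is fair as to intent. At two years or more, however, the written rule has no step that separates menopause from contraception.
- **Other cover** applies whatever her class. Pregnancy or intended pregnancy excludes (4.1.2). Pregnancy stops treatment (4.6.1), must be reported within 24 hours (5.4) and is followed to outcome (5.5.1). Her contraceptive is recorded as a concomitant medication (4.4), and Section 4.4.2.4 sends investigators to the prescribing information. Apart from the bar on intended pregnancy, the pregnancy rules act once a pregnancy is known. The medication provisions may alert the investigator but order no test. The consent form itself is not available to check.

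An investigator may well test and counsel her anyway. The point concerns what the protocol requires.

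**Conclusion.** The point holds as a fault in the rule itself. A fertile woman whose amenorrhoea of two years or more is due to a hormonal method is left outside childbearing potential without a test. The pregnancy tests, egg-donation rule and consent instruction do not attach to her, and the two-method and barrier duty does not clearly attach.

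Three stronger readings are tempting but unsupported:

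- That such women are expected in the trial. The documents show only that users of hormonal contraception may enrol; nothing shows any with two years of amenorrhoea.
- That the 239 to 519 days are unprotected. She is using a method from a list with stated failure rates below 1% per year; what remains is an interaction that may reduce its effect.
- That a menstruating woman with one ovary removed is released in the same way. The unqualified word oophorectomy leaves her unclassified, but the negative rule does not cover her.

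The reach is narrow. Cohort 1 takes no new patients (Section 4.2), the vemurafenib warning concerns Cohort 2, and the assumed 0.4 to 3 women may in fact be none. No statistical result changes. The correction should still be made, because the hazard is one the protocol itself identifies and the change is very small.

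**What to change.** In the Synopsis, Section 4.1.1 and Section 4.5.9, limit both the amenorrhoea rule and the two-year FSH waiver to amenorrhoea with no cause other than menopause, expressly excluding hormonal contraception and other drug or medical causes. Add that a woman with intact ovaries and uterus who is amenorrhoeic on a hormonal method is of childbearing potential. Align note o of Appendix 2, and note n of Appendix 1 for any Cohort 1 patient still on treatment. Writing bilateral oophorectomy would be an optional clarification.

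The cost is a short wording change in three places and two notes. Each reclassified woman would have k + 2 routine pregnancy tests through discontinuation (4 to 14 under the assumed cycles, about 1 to 42 across the trial), the follow-up tests to six months, and a barrier method. All of these are already in the protocol for other women.
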